2.0 TRIAL DESIGN

[figure not shown]
Open label phase I trial. Primary objective is to determine the recommended phase 2 dose (RP2D) of the combination of spartalizumab and siltuximab. The design is 3+3 with 3 dose levels of siltuximab. Maximal Tolerated Dose (MTD) is defined as the dose at which less than one-third of the subjects experience a DLT in the first 6 weeks of treatment.

After determining the RP2D, an additional 24 patients with pancreatic cancer will be enrolled in an expansion phase to confirm toxicity profile and obtain paired biopsies. Paired biopsy performed on all patients in each group. Patient must have a primary or metastatic non-bone

Protocol/Version No.: 5, Date December 15, 2022

site that is amenable to safe biopsy. Bone only lesions are not suitable for biopsy. Investigators will discuss with radiologist each case to ensure safety of biopsy procedure.

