6.2.3 Dose limiting toxicity (DLT)

A dose-limiting toxicity (DLT) is defined as an adverse event or abnormal laboratory value assessed as at least possibly related to study treatment that occurs within the first 6 weeks and meets any of the criteria included in Table 7. National Cancer Institute Common Terminology Criteria for Adverse events (NCI CTCAE) version 4.03 will be used for all grading.

The investigator must notify the Sponsor immediately of any unexpected CTCAE grade ≥ 3 adverse events or laboratory abnormalities. Prior to enrolling patients into a higher dose level, CTCAE grade ≥ 2 adverse events will be reviewed for all patients at the current dose level.

Table 7 Criteria for defining dose-limiting toxicities

Table / Criteria for defining dose mining toxicities					
DLT CRITERIA					
Thrombocytopenia Grade 3 with clinically significant bleeding					
Thrombocytopenia Grade 4					
Neutropenia Grade 4 lasting more than 8 days					
Febrile neutropenia CTCAE Grade ≥ 3					
Diarrhea CTCAE Grade $\geq 3 \geq 72$ hrs., despite the use of anti-diarrhea therapy					
Nausea/ vomiting CTCAE Grade \geq 3 \geq 72 hrs., despite the use of anti-emetic therapy					
• CTCAE Grade 2 pneumonitis if it persists > 7 days despite treatment with corticosteroids.					
• Second episode of grade 2 pneumonitis of any duration					
• Grade 3-4 pneumonitis of any duration					
• CTCAE Grade 3 immune-related toxicities that persist > 14 days with same severity despite treatment with corticosteroids.					
• Immune-related toxicities CTCAE Grade 4 of any duration					
Grade 3-4 infusion reaction					

Protocol/Version No.: 5, Date December 15, 2022

- Other non-hematologic treatment-related toxicity at Grade 3 or higher
- Any AE that leads to permanent discontinuation of siltuximab or spartalizumab
- Death
- 6.2.4 Dose expansion 24 patients will be treated on the dose expansion at the RP2D dose.
- 6.2.5 Duration of therapy: Subjects may withdraw consent at any time for any reason or be dropped from the trial at the discretion of the investigator should any untoward effect occur. In addition, a subject may be withdrawn by the investigator if enrollment into the trial is inappropriate, the trial plan is violated, or for administrative and/or other safety reasons. A subject must be discontinued from the trial for any of the following reasons:
 - The subject or legal representative (such as a parent or legal guardian) withdraws consent.

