7.0 TRIAL FLOW CHART

7.1 Study Flow Chart

Trial Period:	Treatment Cycles ^a									End of Treatment Post-Treatment			ıt
	Main Study					To be repeated beyond 8 cycles				~ 0	- 11	Survival	
Treatment Cycle/Title:	Screening (Visit 2)	1	2	3	4	5	6	7	8	Discon	Safety Follow-up	Follow Up Visits ^b	Follow- Up
Scheduling Window (Days):	-28 to -1		± 3	± 3	± 3	± 3	± 3	± 3	± 3	At time of Discon	30 days post discon		Every 12 weeks
Informed Consent	X												
Inclusion/Exclusion Criteria	X												
Demographics and Medical History	X		X	X	X	X	X	X	X	X	X	X	
Prior and Concomitant Medication Review	X	X	X	X	X	X	X	X	X	X	X	X	
Trial Treatment Administration ^c		X	X	X	X	X	X	X	X				
Post-study anticancer therapy status											X	X	
Survival Status	X	X	X	X	X	X	X	X	X	X	X	X	X
Review Adverse Events			X	X	X	X	X	X	X	X	X	X	
Full Physical Examination	X	X	X	X	X	X	X	X	X				
Directed Physical Examination										X	X	X	
Vital Signs and Weight	X	X	X	X	X	X	X	X	X	X	X	X	
ECOG Performance Status	X ^d	X	X	X	X	X	X	X	X	X	X	X	
Pregnancy Test – Urine or Serum β-HCGe	X												
PT/INR and aPTT	X												

Trial Period:	Treatment Cycles ^a								End of Treatment	Post-Treatment			
	Main Study					To b	e repeat	ted beyo	ond 8				Survival
Treatment Cycle/Title:	Screening (Visit 2)	1	2	3	4	5	6	7	8	Discon	Safety Follow-up	Follow Up Visits ^b	Follow- Up
Scheduling Window (Days):	-28 to -1		± 3	± 3	± 3	± 3	± 3	± 3	± 3	At time of Discon	30 days post discon		Every 12 weeks
CBC with Differential	X	X	X	X	X	X	X	X	X	X	X	X	
Comprehensive Serum Chemistry Panel	X	X	X	X	X	X	X	X	X	X	X	X	
Hepatitis screening f	X												
Urinalysis	X									X			
T3, FT4 and TSH	X		X			X			X	X	X		
ECG	X												
Uric Acid	X		X		X		X						
Tumor Imaging	Xg			Xg			Xg						
Archival or Newly Obtained Tissue Collection ⁱ	X	X											
Correlative Studies Blood Collection j	X	X	X	X						X			

- a. Treatment cycles are 3 weeks
- b. Only for patients with ongoing treatment related toxicities. Details of required follow up visit are given in section 6.5.1 and 6.7.
- c. Siltuximab and spartalizumab given day 1 of each cycle except cycle 1 in the expansion phase
- d. ECOG performance status should be done within 10 days or less from day 1 of cycle 1
- e. Pregnancy test once a month women of child bearing potential

Protocol Study No: Winship4463-18 66

Product: Siltuximab plus Spartalizumab

Protocol/Version No.: 5, Date December 15, 2022

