8.1.3 Treatment period

Day 1 (±3 days) of each cycle

- Record concomitant medications
- Vitals (temperature, HR, BP and RR)
- History and physical exam
- ECOG performance status
- Toxicity assessment
- Laboratory Assessments
 - Hematology hemoglobin, hematocrit, red blood cell count, white blood cell count with differential and platelet count

71

Protocol Study No:

Product: Siltuximab and Spartalizumab

Protocol/Version No.: 5, Date December 15, 2022

 Chemistry sodium, potassium, chloride, bicarbonate, magnesium, calcium, phosphorus, blood urea nitrogen, creatinine, glucose (random), total bilirubin, LDH, total protein, ALP, ALT, AST, and albumin

- o Tumor markers when applicable
- o T3, FT4, TSH cycle 2 and then after every 3 cycle
- o Uric acid every other cycle
- o For the cycle1 day 1 labs, blood samples from the screening tests maybe used if completed within 1 week of day 1
- Blood sample 20 cc for correlative work (only cycle 1, 2, 3)
- Spartalizumab and siltuximab will be administered as IV infusion every 3 weeks. Given the variability of infusion pumps, a window of -5 minutes and +10 minutes is permitted.
- In selected case in patients receiving paired biopsies siltuximab maybe held in cycle 1

Days 8 and 15 (± 1 day) in cycle 1 and 2 ONLY

- Record concomitant medications
- Vitals (temperature, HR, BP and RR)
- History and physical exam
- ECOG performance status
- Toxicity assessment
- Blood sample 20 cc for correlative work (only cycle1)
- Laboratory Assessments
 - Chemistry sodium, potassium, chloride, bicarbonate, magnesium, calcium, phosphorus, blood urea nitrogen, creatinine, glucose (random), total bilirubin, LDH, total protein, ALP, ALT, AST, and albumin

Between days 14-21 cycle 1

• Repeat biopsy in selected cases.

Every Month

Pregnancy test for women of child bearing potential

72

Product: Siltuximab and Spartalizumab

Protocol/Version No.: 5, Date December 15, 2022

Every 3 cycles between day 15 and 21

• Repeat cross sectional imaging (CT or MRI)

End of treatment visit

- Vitals (temperature, HR, BP and RR)
- History and physical exam
- ECOG performance status
- Toxicity assessment
- Laboratory Assessments
 - Hematology hemoglobin, hematocrit, red blood cell count, white blood cell count with differential and platelet count
 - Chemistry sodium, potassium, chloride, bicarbonate, magnesium, calcium, phosphorus, blood urea nitrogen, creatinine, glucose (random), total bilirubin, LDH, total protein, ALP, ALT, AST, and albumin

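### No blood count is scheduled on days 8 and 15 of cycles 1 and 2, so silent Grade 4 cytopenias that count as DLTs may be missed; any bias favours escalation, but its size is unknown

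*Combined protocol and SAP*

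**What the plan says.** Section 2.0 defines the MTD as "the dose at which less than one-third of the subjects experience a DLT in the first 6 weeks of treatment". Table 7 in Section 6.2.3 has four hematologic criteria. Two have a clinical trigger: "Thrombocytopenia Grade 3 with clinically significant bleeding" and "Febrile neutropenia CTCAE Grade ≥ 3". The other two can be met on laboratory values alone: "Thrombocytopenia Grade 4", with no minimum duration, and "Neutropenia Grade 4 lasting more than 8 days".

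Section 8.1.3 lists hematology and chemistry on day 1 of each cycle and at end of treatment. Under "Days 8 and 15 (± 1 day) in cycle 1 and 2 ONLY" it lists vital signs, examination, performance status, toxicity assessment, chemistry and (cycle 1 only) a correlative sample. Hematology is not listed. According to the flow chart notes in Section 7.1, the correlative sample is for immune-cell subsets.

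In the Section 7.1 flow chart, the row "CBC with Differential" is marked once per cycle, and the notes state "Treatment cycles are 3 weeks". The chart has no day 8 or day 15 column. Section 8.1.3 also lets a screening sample up to one week old serve as the cycle 1 day 1 count.

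**The concern.** Two DLT criteria depend on a test that the plan takes only every 21 days during the DLT window. A patient could have a Grade 4 cytopenia without symptoms between day 1 visits and be recorded as DLT-free.

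Under Section 6.2.2, escalation turns on whether 0, 1 or at least 2 of 3 to 6 patients have a DLT, so a single missed event can change a decision. The error runs one way: a missing count can remove a DLT from the tally but cannot add one. The expansion stopping rule in Section 12.1, which counts DLTs over 8 weeks in the first 12 patients, relies on the same schedule.

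**Working it through.** **The plan's own figures.** The documents give no figure for how often a DLT would be detected, so there is none to reproduce on that point. The escalation sample size in Section 12.1 does reproduce: one level stopped after 3 patients gives 3, and three levels of 6 give 18.

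**Step 1: when counts are taken.** With 21-day cycles and day 1 counts only, the scheduled counts are on day 1, day 22 (±3) and day 43 (±3). The 6-week window is days 1-42. Day 22 is clearly inside it and day 43 is at its edge. An episode of up to 20 days (days 2-21 or 23-42) can fall wholly between counts.

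**Step 2: chance that a scheduled count falls within an episode.** Assume uniform onset. For an episode of d days and a gap of g days between counts, the chance is min(1, d/g).

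| Episode length | As written (g = 21) | Weekly (g = 7) |
|---|---|---|
| 5 days | 5/21 = 24% | 5/7 = 71% |
| 9 days (shortest whole number above 8) | 9/21 = 43% | 100% |
| 10 days | 10/21 = 48% | 100% |
| 14 days | 14/21 = 67% | 100% |
| 20 days | 20/21 = 95% | 100% |

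A day-by-day check, with onset uniform over days 2-42 and counts on days 22 and 43, gives 22% for 5-day and about 41% for 9-day episodes. If only the day 22 count belongs to the window, these fall to 12% and 22%.

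**Step 3: seeing an episode is not the same as dating it.** The neutropenia criterion needs more than 8 days. If duration runs from the first observed Grade 4 count and repeat counts follow, the chance of showing it is min(1, (d-8)/g).

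- 9 days: 1/21 = 5% as written; 1/7 = 14% weekly.
- 14 days: 6/21 = 29% as written; 6/7 = 86% weekly.

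Weekly counts without repeats never show it for episodes of 14 days or less, because two counts 7 days apart do not span more than 8 days.

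**Step 4: effect on one 3+3 level.** A level passes with 0 of 3 DLTs, or 1 of 3 followed by 0 of 3:

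P(pass) = (1-p)^3 + 3p(1-p)^5

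Assume a 15% non-hematologic DLT risk, independent of a hematologic risk h. The true rate is p = 1 - 0.85(1-h). The apparent rate is 1 - 0.85(1-hs), where s is the detection chance, from 5/21 to 10/21 (5-day to 10-day episodes). A single sighting is counted as a detected DLT, which is generous to the schedule for neutropenia.

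| h (assumed) | True rate | Apparent rate | Pass, all DLTs seen | Pass, as written |
|---|---|---|---|---|
| 4% | 1 - 0.85×0.96 = 18.4% | 15.8-16.6% | 74% | 78-80% |
| 8% | 1 - 0.85×0.92 = 21.8% | 16.6-18.2% | 67% | 75-78% |
| 20% | 1 - 0.85×0.80 = 32.0% | 19.0-23.1% | 45% | 64-73% |

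If no DLT is a silent hematologic one, the pass probability does not change.

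**The case against.** The strongest reply is that the effect may be small.

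- In Table 3 of Section 4.1.2.1, Grade 3-4 thrombocytopenia on siltuximab 11 mg/kg was 2/53 (4%), against 1/26 (4%) on placebo, over the first 8 infusions. Only part of that would be a DLT.
- Section 4.1.1.2 reports no DLTs for single-agent spartalizumab in dose escalation, and neither neutropenia nor thrombocytopenia among its most frequent events.
- Section 4.1.2.1 calls neutropenia very common with siltuximab but gives no grade.

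This stands. It makes the 20% row a high case, although the documents do not exclude a higher rate for the combination.

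The plan also has safeguards. Patients are examined on days 8 and 15, Section 8.1 allows unscheduled procedures when the investigator thinks them necessary, and Table 8-8 recommends counts every 3-5 days once Grade 4 neutropenia is known. Long episodes are mostly seen even as written. These points limit the problem to silent episodes that resolve between counts. They do not remove it, because none of them schedules the count that would first find such an episode.

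Three stronger readings are tempting. A reader might infer that DLTs are in fact being undercounted; without incidence or duration data the documents support only a risk. The primary objective is the RP2D, which missed DLTs reach only through the escalation rule. A reader might also infer that weekly counts would settle the neutropenia criterion; Step 3 shows that they would not on their own. Finally, a reader might take the flow chart as proof that the count was deliberately left out. It has no day 8 or 15 column at all, so it also omits the chemistry that Section 8.1.3 requires on those days.

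**Conclusion.** The point holds as a risk of missed DLTs. Sections 7.1 and 8.1.3 do not schedule the test needed to ascertain reliably two of the DLT criteria in Section 6.2.3. The direction is certain: any error is toward too few DLTs and favours escalation. The size cannot be computed from the documents. Under the stated assumptions (uniform onset, 5- to 10-day silent episodes, 15% independent non-hematologic risk), the pass probability for a level rises by about 4-5 points at 4% hematologic risk and by about 19-27 points at 20%. Neither hematologic rate is given in the documents as a DLT rate for the combination. The DLT criteria with clinical triggers, and the non-hematologic ones, are largely or wholly unaffected. This is a worthwhile and inexpensive improvement to the plan; no stated figure is shown to be wrong.

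**What to change.** Add a CBC with differential and platelet count to the laboratory list for days 8 and 15 of cycles 1 and 2 in Section 8.1.3, drawn with the chemistry sample already scheduled, and show these visits and the count in the Section 7.1 flow chart.

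Reconcile Sections 6.2.3, 7.1 and 8.1.3 on two further points:

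- whether the cycle 3 day 1 count belongs to the 6-week DLT window;
- how the duration of Grade 4 neutropenia is dated between counts, using the repeat counts that Table 8-8 already describes.

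The cost is one extra tube at four existing draws per patient, with no new visit or needle-stick. Slightly more cytopenias will be recorded.

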8.1.3.1 Second Course Phase (Retreatment Period)

Subjects who stop siltuximab and spartalizumab with SD or better may be eligible for up to one year of additional siltuximab and spartalizumab therapy if they progress after stopping study treatment. This retreatment is termed the Second Course Phase of this study and is only available if the study remains open and the subject meets the following conditions:

Either

- O Stopped initial treatment with siltuximab and spartalizumab after attaining an investigator-determined confirmed CR according to RECIST 1.1, and
 - Was treated for at least 24 weeks with siltuximab and spartalizumab before discontinuing therapy
 - Received at least two treatments with siltuximab and spartalizumab beyond the date when the initial CR was declared

OR

o Had SD, PR or CR and stopped siltuximab and spartalizumab treatment after 24 months of study therapy for reasons other than disease progression or intolerability

Product: Siltuximab and Spartalizumab

Protocol/Version No.: 5, Date December 15, 2022

AND

• Experienced an investigator-determined confirmed radiographic disease progression after stopping their initial treatment with siltuximab and spartalizumab

- Did not receive any anti-cancer treatment since the last dose of siltuximab and spartalizumab
- Has a performance status of 0 or 1 on the ECOG Performance Scale
- Patients should not be restarted on the study treatments if urgent treatment of the tumor(s) is needed to avoid risk to organ function or physical function (e.g. visceral crisis or spinal cord compression).
- Meet all the eligibility criteria as detailed in Section 6.1

Subjects who restart treatment will be retreated at the same dose and dose interval as when they last received siltuximab and spartalizumab. Treatment will be administered for up to one additional year.

Visit requirements are outlined in Section 7.0 – Trial Flow Chart.

9.0 SAFETY MONITORING AND REPORTING-NOVARTIS

9.1 Adverse events

9.1.1 Definitions and reporting

An adverse event is defined as the appearance of (or worsening of any pre-existing) undesirable sign(s), symptom(s), or medical condition(s) that occur after patient's signed informed consent has been obtained. Abnormal laboratory values or test results occurring after informed consent constitute adverse events only if they induce clinical signs or symptoms, are considered clinically significant, require therapy (e.g., hematologic abnormality that requires transfusion or hematological stem cell support), or require changes in study medication(s).

Adverse events that begin or worsen after informed consent should be recorded in the Adverse Events CRF. Conditions that were already present at the time of informed consent should be recorded in the Medical History page of the patient's CRF. Adverse event monitoring should be continued for at least:

- 150 days following the last dose of spartalizumab (or all patients in a double blind study) OR
- until the start of a new post treatment antineoplastic medication if sooner than the 150 days mentioned above. If a patient starts a post treatment antineoplastic therapy, then

Product: Siltuximab and Spartalizumab

Protocol/Version No.: 5, Date December 15, 2022

only adverse events suspected to be related to study treatment should be collected out to 150 days after discontinuation of spartalizumab.

Adverse events (including lab abnormalities that constitute AEs) should be described using a diagnosis whenever possible, rather than individual underlying signs and symptoms. When a clear diagnosis cannot be identified, each sign or symptom should be reported as a separate Adverse Event.

Adverse events will be assessed and graded according to the Common Terminology Criteria for Adverse Events (CTCAE) version

Grade 1 to 5 will be used to characterize the severity of the Adverse Event.

If CTCAE grading does not exist for an adverse event, the severity of mild, moderate, severe, and life-threatening, death related to the AE corresponding respectively to Grades 1 - 5, will be used. Information about any deaths (related to an Adverse Event or not) will also be collected through a Death form (or EOT/SEC/Survival Information in NOVDD).

The occurrence of adverse events should be sought by non-directive questioning of the patient (patient) during the screening process after signing informed consent and at each visit during the study. Adverse events also may be detected when they are volunteered by the patient (patient) during the screening process or between visits, or through physical examination, laboratory test, or other assessments. As far as possible, each adverse event should be evaluated to determine:

- 1. The severity grade (CTCAE Grade 1-5)
- 2. Its duration (Start and end dates)
- 3. Its relationship to the study treatment (Reasonable possibility that AE is related: No, Yes) or
 - Its relationship to the study treatment (Reasonable possibility that AE is related: No, Yes, investigational treatment, Yes, the study treatment (non-investigational), Yes, both and/or indistinguishable)
- 4. Action taken with respect to study or investigational treatment (none, dose adjusted, temporarily interrupted, permanently discontinued, unknown, not applicable)
- 5. Whether medication or therapy was given (no concomitant medication/non-drug therapy, concomitant medication/non-drug therapy)
- 6. Whether it is serious, where a serious adverse event (SAE) is defined as in Section 9.2 and which seriousness criteria have been met (include for NCDS trials)

Outcome (not recovered/not resolved, recovered/resolved, recovering/resolving, recovered/resolved with sequelae, fatal, unknown)

If the event worsens the event should be reported a second time in the CRF noting the start date when the event worsens in toxicity. For grade 3 and 4 adverse events only, if improvement

Protocol/Version No.: 5, Date December 15, 2022

to a lower grade is determined a new entry for this event should be reported in the CRF noting the start date when the event improved from having been Grade 3 or Grade 4.

76

For phase I studies any AE that constitutes a DLT should be reported like a grade 3 and 4 adverse event.

All adverse events should be treated appropriately. If a concomitant medication or non-drug therapy is given, this action should be recorded on the Adverse Event CRF.

Once an adverse event is detected, it should be followed until its resolution or until it is judged to be permanent, and assessment should be made at each visit (or more frequently, if necessary) of any changes in severity, the suspected relationship to the study treatment, the interventions required to treat it, and the outcome.

Progression of malignancy (including fatal outcomes), if documented by use of appropriate method (for example, as per RECIST criteria for solid tumors), should not be reported as a serious adverse event.

Adverse events separate from the progression of malignancy (example, deep vein thrombosis at the time of progression or hemoptysis concurrent with finding of disease progression) will be reported as per usual guidelines used for such events with proper attribution regarding relatedness to the drug.

9.1.2 Laboratory test abnormalities

9.1.2.1 Definitions and reporting

Laboratory abnormalities that constitute an Adverse event in their own right (are considered clinically significant, induce clinical signs or symptoms, require concomitant therapy or require changes in study treatment), should be recorded on the Adverse Events CRF. Whenever possible, a diagnosis, rather than a symptom should be provided (e.g. anemia instead of low hemoglobin). Laboratory abnormalities that meet the criteria for Adverse Events should be followed until they have returned to normal or an adequate explanation of the abnormality is found. When an abnormal laboratory or test result corresponds to a sign/symptom of an already reported adverse event, it is not necessary to separately record the lab/test result as an additional event.

Laboratory abnormalities, that do not meet the definition of an adverse event, should not be reported as adverse events. A Grade 3 or 4 event (severe) as per CTCAE does not automatically indicate a SAE unless it meets the definition of serious as defined below and/or as per investigator's discretion. A dose hold or medication for the lab abnormality may be required by the protocol in which case the lab abnormality would still, by definition, be an adverse event and must be reported as such.

